### 6.3 Eligibility for the OLE Period

Prior to entering the OLE Period, subjects on double-blind study treatment must complete all of the Week 48 visit assessments. Prior to initiating the OLE Period assessments, all subjects will be asked to read and sign a separate ICF. To be eligible to participate in the OLE Period of this study, the subject must have completed the double-blind Treatment Period without meeting any withdrawal criteria and have been compliant with the ongoing clinical study requirements.

## 6.4 Eligibility for the OLE2 Period

Prior to initiating the OLE2 Period assessments, all subjects will be asked to read and sign a separate ICF.

### 6.4.1 All subjects (OLE2 Groups A and B)

To be eligible to participate in the OLE2 Period, all of the following inclusion criteria must be confirmed for all subjects:

1. Subject provided informed consent.
2. Subject is considered reliable and capable of adhering to the protocol (eg, able to understand and complete diaries), visit schedule, and medication intake according to the judgment of the Investigator.
3. Subject completes the OLE Period to Week 144 without meeting any withdrawal criteria defined in Section 6.5.

### 6.4.2 OLE2 Period Group A subjects

To participate in the OLE2 Period, subjects still treated in the OLE Period and who completed the Week 144 Visit by the time of the implementation of Protocol Amendment #5.4 will not need to fulfil other eligibility criteria than those listed in Section 6.4.1 and will continue their treatment from the Week 144/OLE2 Baseline Visit if they do not meet any of the withdrawal criteria defined in Section 6.5.

### 6.4.3 OLE2 Period Group B subjects

#### *Inclusion criteria*

To be eligible to participate in the OLE2 Period, all of the additional following inclusion criteria must be confirmed during the OLE2 Screening Period for subjects who have attended Week 144 and are in the SFU or have completed the SFU before Protocol Amendment #5.4 implementation:

1. Female subjects must be:
  - Postmenopausal: Menopause is defined as 12 consecutive months of amenorrhea, for which there is no other obvious pathological or physiological cause.
  - Permanently sterilized (eg, tubal occlusion, hysterectomy, bilateral salpingectomy)
  - Or, if of childbearing potential (and engaged in sexual activity that could result in procreation), must be willing to use a highly effective method of contraception throughout the duration of the study until 20 weeks after last administration of IMP, and have a negative pregnancy test at OLE2 Screening. The following methods are considered highly effective when used consistently and correctly
    - Combined (estrogen and progestogen) hormonal contraception associated with inhibition of ovulation (oral, intravaginal, or transdermal)
    - Progestogen-only hormonal contraception associated with inhibition of ovulation (oral, injectable, implantable)
    - Intrauterine device

- 
- Intrauterine hormone-releasing system
  - Vasectomized partner
  - Abstinence as a form of birth control is generally not allowed in the study unless abstinence is in accordance with a subject's preferred and common lifestyle. Study personnel must confirm the continued use of abstinence is still in accordance with the subject's lifestyle at regular intervals during the study.
2. Subjects with a diagnosis of Crohn's disease or ulcerative colitis are allowed as long as they have no active symptomatic disease.

### ***Exclusion criteria***

Subjects in the OLE2 Group B are not permitted to enroll in the OLE2 Period if any of the following exclusion criteria is met:

1. Female subjects who plan to become pregnant during the OLE2 Period or within 20 weeks following final dose of study medication.
2. Subject has developed any medical or psychiatric condition that, in the opinion of the Investigator, could jeopardize or would compromise the subject's ability to participate in the OLE2 Period.
3. Any subjects with an ongoing SAE, or a history of serious infections, the Medical Monitor must be consulted prior to the subject's entry in the OLE2 Period, although the decision on whether to enroll the subject remains with the Investigator.
4. Subject had a positive or indeterminate IGRA in the OLE study to Week 144, unless appropriately evaluated and treated as per Section 12.3.1.
5. Subject may not participate in another study of a medicinal product or device under investigation
6. Subject has a history of chronic alcohol or drug abuse within 6 months prior to reentry as assessed by medical history, site interview, and/or results of the urine drug screen.
7. Subjects who have used systemic treatments after Week 144 must have stopped this treatment 1 month prior to receiving the first bimekizumab injection in the OLE2 Period (See Section 7.8.2 regarding prohibited medications).
8. Subject has erythrodermic, guttate, or pustular form of PSO.
9. Subject is noncompliant with the study procedures or medications in the opinion of the Investigator.
10. Subject has a clinical laboratory value meeting any of the following criteria:
  - a.  $\geq 3.0x$  ULN of any of the following: ALT, AST, alkaline phosphatase (ALP); or  $>ULN$  total bilirubin ( $\geq 1.5xULN$  total bilirubin if known Gilbert's syndrome)
  - b. A laboratory value meeting any of the following criteria:
    - Absolute neutrophil count  $< 1.0 \times 10^3/\mu L$

- Absolute lymphocyte count  $<0.2 \times 10^3/\mu\text{L}$

Subjects may enter the OLE2 Period if the result is transient. If a retest is required, it must be done within 1 to 2 weeks.

11. Subject has concurrent acute or chronic viral hepatitis B or C or HIV infection. Subjects who have evidence of, or tested positive for hepatitis B or hepatitis C are excluded. A positive test for the hepatitis B virus is defined as: (1) positive for hepatitis B surface antigen or (2) positive for anti-hepatitis B core antibody. A positive test for the hepatitis C virus (HCV) is defined as: (1) positive for hepatitis C antibody (HCV Ab) and (2) positive via a confirmatory test for HCV (for example, HCV polymerase chain reaction).
12. There is confirmation of a pregnancy, as evidenced by a positive pregnancy test (see [Section 12.1.4](#) for more information regarding pregnancies).
13. Subjects showing:
  - Suicidal ideation in the past month prior to the OLE2 Screening Visit as indicated by a positive response ("Yes") to either Question 4 or Question 5 of the eC-SSRS.
  - Any suicidal behavior since last visit.
14. Subject has presence of moderately severe or severe major depression, indicated by a score  $\geq 15$  on the PHQ-9. Medication used to treat depression should be stable for 4 weeks prior to Week 144/OLE2 Baseline.
15. Subject has developed any active malignancy or history of malignancy prior to the OLE2 Screening Visit EXCEPT treated and considered cured cutaneous squamous or basal cell carcinoma, or in situ cervical cancer.
16. Subject has received any live (includes attenuated) vaccination within the 8 weeks prior to the Week 144/OLE2 Baseline Visit.

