### 5.2.3 OLE Period

After completion of the Week 48 visit assessments, subjects will be allowed to enroll in the OLE Period. All subjects enrolling in the OLE Period will sign a new ICF, and then receive the following IMP regimens as determined by the subject's treatment regimen and PASI response in the double-blind Treatment Period.

At Week 48, subjects receiving:

- Bimekizumab 320mg Q4W who achieve PASI90 at Week 48 of the double-blind Treatment Period will be randomized 1:1 to receive bimekizumab 320mg Q4W or bimekizumab 320mg Q8W.
- Bimekizumab 320mg Q4W who do not achieve PASI90 at Week 48 of the double-blind Treatment Period will receive bimekizumab 320mg Q4W.
- Bimekizumab 320mg Q8W who do not achieve PASI90 at Week 48 of the double-blind Treatment Period will receive bimekizumab 320mg Q4W.
- Bimekizumab 320mg Q8W who achieve PASI90 at Week 48 of the double-blind Treatment Period will receive bimekizumab 320mg Q8W.
- Secukinumab who do not achieve PASI90 at Week 48 of the double-blind Treatment Period will receive bimekizumab 320mg Q4W.
- Secukinumab who achieve PASI90 at Week 48 of the double-blind Treatment Period will be randomized 1:1 to receive bimekizumab 320mg Q4W or bimekizumab 320mg Q8W.

During the OLE Period, subjects will attend study visits at Weeks 52, 56, 64, and 72, and then every 12 weeks. At study visits, IMP will be administered in the clinic by sc injection as applicable. In between study visits, subjects will self-inject IMP at home.

The subject's dosing interval will change from bimekizumab 320mg Q4W to bimekizumab 320mg Q8W at Week 64, or at the next scheduled clinic visit after implementation of Protocol Amendment #5.1 if the subject has already completed Week 64.

The last dose bimekizumab 320mg Q8W in the OLE Period will be administered at Week 136. The End of Treatment Visit of the OLE Period will be the Week 144 Visit.

All subjects not enrolling in the open-label study will have the Week 48 study assessments and will enter the SFU Period.

The assessments to be performed at each OLE Period visit are presented in [Table 5–2](#).

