### **5.3 Study duration per subject**

For each subject, the study will last a maximum of up to 165 weeks, as follows:

- Screening Period: 2 to 5 weeks
- Double-blind Treatment Period: 48 weeks (final dose at Week 44)
- OLE Period: 96 weeks (final dose at Week 136 for subjects receiving bimekizumab 320mg Q8W and at Week 140 for subjects receiving bimekizumab 320mg Q4W) followed by a Safety Follow-Up Period: a SFU Visit is planned 20 weeks after the final dose of IMP visit in the OLE Period (this SFU will not apply to subjects directly rolling over from the OLE to the OLE2 Period [see Section 5.2.5])

Subjects eligible for the OLE2 Period (added as part of Protocol Amendment #5.4) will enter the OLE2 Period after completing Week 144 of the OLE Period. The OLE2 Period will include a 48-week treatment period with a final visit at OLE2 Week 48 and a SFU Period (SFU2) of 20 weeks after the final dose of IMP administered in the OLE2 Period.

For the subjects in the OLE2 Period, maximum study duration will depend on the time between their participation in the OLE until Week 144 and the start of the OLE2 Period:

- 209 weeks for subjects still being treated in the OLE Period and who will directly roll over to the OLE2 Period at Week 144
- 225 weeks for subjects who have completed Week 144 and the SFU; these subjects will have a 4-week Screening Period before reinitiating treatment in the OLE2 Period. Note: for these subjects, the study duration will not be continuous.
- Between 209 and 225 weeks for subjects who have completed Week 144 and are participating in the SFU. For these subjects, the maximum study duration will depend upon when they stop the 20-week SFU period to enter the 4-week OLE2 Screening Period.

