## 6.2 Exclusion criteria

Subjects are not permitted to enroll in this study if any of the following criteria are met:

1. Female subject who is breastfeeding, pregnant, or plans to become pregnant during the study or within 20 weeks following the final dose of IMP.
2. Subject previously participated in a bimekizumab clinical study and received at least 1 dose of the IMP (including placebo).
3. Subject is currently participating in another study of a medication (systemic) under investigation. Subject must be washed out of the medication for 12 weeks or at least 5 half-lives prior to the Baseline Visit, whichever is greater.

4. Subject is currently participating in another study of a topical medication under investigation. Subject must be washed out of the medication for 4 weeks prior to the Baseline Visit.
5. Subject is currently, or was within the 4 weeks prior to the Baseline Visit, participating in another study of a medical device under investigation.
6. Subject has a known hypersensitivity to any excipients of bimekizumab or secukinumab.
7. Subject has a form of PSO other than chronic plaque-type (eg, pustular, erythrodermic and guttate PSO or drug-induced PSO).
8. Subject has an active infection or history of infection(s) as follows:
  - Any active infection (except common cold) within 14 days prior to Baseline
  - A serious infection, defined as requiring hospitalization or iv anti-infective(s) within 2 months prior to the Baseline visit
  - A history of opportunistic, recurrent, or chronic infections that, in the opinion of the Investigator, might cause this study to be detrimental to the subject. Opportunistic infections are infections caused by uncommon pathogens (eg, pneumocystis jirovecii, cryptococcosis) or unusually severe infections caused by common pathogens (eg, cytomegalovirus, herpes zoster)
9. Subject has concurrent acute or chronic viral hepatitis B or C or human immunodeficiency virus (HIV) infection. Subjects who have evidence of, or tested positive for hepatitis B or hepatitis C are excluded. A positive test for the hepatitis B virus is defined as: (1) positive for hepatitis B surface antigen or (2) positive for anti-hepatitis B core antibody. A positive test for the hepatitis C virus (HCV) is defined as: (1) positive for hepatitis C antibody (HCV Ab) and (2) positive via a confirmatory test for HCV (for example, HCV polymerase chain reaction).

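### The re-entry criteria for OLE2 Group B drop breastfeeding from the exclusion that applied at first entry, so no criterion stops a breastfeeding subject from being re-dosed

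*Protocol*

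**What the plan says.** At first entry, Section 6.2 criterion 1 excludes a "Female subject who is breastfeeding, pregnant, or plans to become pregnant during the study or within 20 weeks following the final dose of IMP". That is three separate states in one criterion.

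Section 6.4.3 sets out separate inclusion and exclusion criteria for OLE2 Group B. On reproductive status it contains:

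- exclusion 1: "Female subjects who plan to become pregnant during the OLE2 Period or within 20 weeks following final dose of study medication";
- exclusion 12: "There is confirmation of a pregnancy, as evidenced by a positive pregnancy test";
- inclusion 1, for subjects of childbearing potential: highly effective contraception "throughout the duration of the study until 20 weeks after last administration of IMP, and have a negative pregnancy test at OLE2 Screening".

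The criteria common to all OLE2 subjects are in Section 6.4.1. The only one that looks back at events is criterion 3: "Subject completes the OLE Period to Week 144 without meeting any withdrawal criteria defined in Section 6.5".

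Section 5.3 notes that, where the Safety Follow-Up (SFU) was completed before re-entry, "for these subjects, the study duration will not be continuous".

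**The concern.** Two of the three states barred in Section 6.2 reappear in the Group B list and the third does not. The protocol gives no reason for the difference.

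For Group B the OLE2 Baseline dose is a restart after time off drug, in subjects some of whom have left the study altogether. A site following Section 6.4.3 as written could give bimekizumab to a breastfeeding subject whom the same protocol would refuse at first entry. What is at stake is possible exposure of an infant, together with an eligibility rule that differs between two entries to the same trial. The primary endpoint, the multiplicity procedure and the power are not affected.

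Group A does not have this problem. Those subjects roll over directly while still under study rules, and a pregnancy leads to withdrawal from study drug under Section 6.5 criterion 7.

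**Working it through.** The protocol gives no figure to reproduce. The check compares the text section by section and then asks whether the situation can arise.

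**1. Coverage of the three states**

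| State barred by Section 6.2 criterion 1 | Group B equivalent |
|---|---|
| Plans pregnancy | Section 6.4.3 exclusion 1 |
| Pregnant | Section 6.4.3 exclusion 12, plus the negative test in inclusion 1 |
| Breastfeeding | none |

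Group B faces 3 criteria from Section 6.4.1, 2 inclusion criteria and 16 exclusion criteria from Section 6.4.3: 3 + 2 + 16 = 21. Three of them concern pregnancy (inclusion 1, exclusions 1 and 12) and none concerns breastfeeding. Breastfeeding is also absent from the withdrawal criteria (Section 6.5), the OLE2 Screening procedures (Section 8.4.1) and the pregnancy-testing section (12.3.2).

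**2. Does Section 6.2 still apply at re-entry?** It cannot sensibly do so. Its criterion 21 bars previous secukinumab exposure, which would remove everyone from the original comparator arm. Its criterion 2 bars anyone who has already received study drug in a bimekizumab study. Section 6.4.3 also restates exclusions such as hepatitis and HIV, depression, malignancy and live vaccines, which would be redundant if Section 6.2 carried over. Nothing in Section 6.4.3 refers back to Section 6.2.

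**3. Does another Group B criterion catch it indirectly?**

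- Exclusion 2 depends on a medical or psychiatric condition that affects the subject's ability to take part. Breastfeeding is not plainly such a condition, and the concern is the infant.
- A negative pregnancy test says nothing about a subject who has already given birth.
- Section 6.4.1 criterion 3 considers withdrawal criteria, pregnancy among them, only up to Week 144.

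**4. Can the situation arise?** Section 5.2.3 states: "The last dose bimekizumab 320mg Q8W in the OLE Period will be administered at Week 136". The contraception commitment in Section 6.1 criterion 8 lasts 20 weeks after the last dose, and the SFU Visit is also 20 weeks after it:

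- 136 + 20 = Week 156.

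The time from end of contraception to birth is not in the protocol. It is an assumption, with conception directly after contraception ends:

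| Assumed weeks to birth | Earliest week breastfeeding | Weeks after last dose | Weeks after SFU Visit |
|---|---|---|---|
| 35 | 156 + 35 = 191 | 191 − 136 = 55 | 35 |
| 38 | 156 + 38 = 194 | 194 − 136 = 58 | 38 |
| 40 | 156 + 40 = 196 | 196 − 136 = 60 | 40 |

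**5. Does the protocol limit the break?** Section 5.3 gives a maximum of 225 weeks for subjects who completed the SFU. That total is screening, time to the SFU Visit, OLE2 Screening, OLE2 dosing to Week 40, and the second follow-up: 5 + 156 + 4 + 40 + 20 = 225. It contains no off-study time, and no maximum gap between the SFU and OLE2 Screening is stated. The situation is therefore not ruled out.

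**The case against.** The strongest reply is that the Group B list is meant to be lighter. These subjects have already been treated and observed, and several Section 6.2 exclusions are not repeated for them: recent myocardial infarction or stroke, major surgery, hypersensitivity to excipients, and the white-cell and hemoglobin limits. The neutrophil limit is relaxed from 1.5 to 1.0 × 10³/µL and the lymphocyte limit from 500 cells/µL to 0.2 × 10³/µL. A missing Section 6.2 item is therefore not in itself an error. That is fair. In this case, however, the other two parts of the same criterion were kept, and no reason is given for losing the third.

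Second, entry is not automatic. OLE2 Screening collects new or changed medical history from subjects who completed the SFU, so a recent birth would probably come to light, and the investigator could decline to enroll. This stands as mitigation, and it is why the text supports saying a site *could* dose such a subject, not that it *would*. It does not replace a criterion: Section 6.2 has a broader discretionary exclusion (criterion 20) and still names breastfeeding.

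Third, Section 12.1.4, to which exclusion 12 refers, calls for withdrawal when a subject becomes pregnant after first taking study drug. That narrows the exposed group by dealing with pregnancies that become known during the OLE or SFU. It does not clearly reach a subject who completed the SFU and conceived later.

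Fourth, the remaining case needs a chain of events: SFU completed, conception, birth, continued breastfeeding, and OLE2 entry still open. The protocol gives neither the timing of Amendment 5.4 relative to Week 156 nor the enrollment window, so nobody can show from it that any subject would get that far. This also stands, and it limits the likely size of the problem. The protocol states no specific lactation hazard for bimekizumab either; the case rests on its own decision to bar breastfeeding at first entry.

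**Conclusion.** The concern holds. The Group B criteria keep two of the three states in Section 6.2 criterion 1 and omit breastfeeding, and no other entry, withdrawal or screening provision supplies it. A subject who completed the SFU and has since given birth could meet every written criterion for re-dosing while breastfeeding.

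The timing estimate rests on a last OLE dose at Week 136, adherence to contraception until Week 156, and an assumed 35 to 40 weeks to birth. A compliant subject still in the SFU is not affected. The number of subjects concerned cannot be derived from the protocol and is probably small. This is a patient-safety gap in an eligibility rule, worth correcting because the correction is simple; it has no bearing on the trial's efficacy conclusions.

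**What to change.** In Section 6.4.3, Group B exclusion 1, insert the words *are breastfeeding, or* before *plan to become pregnant*, leaving the rest of the criterion unchanged. Exclusion 12 can stay as it is.

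Confirm the point at OLE2 Screening and again at the Week 144/OLE2 Baseline Visit. Table 5-3 already schedules an eligibility check for Group B at both, so no visit, sample or procedure is added.

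The cost is a few words in one criterion and one line on the OLE2 eligibility checklist. Few subjects, if any, would be lost.

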10. Subject has received any live (includes attenuated) vaccination within the 8 weeks prior to the Baseline visit (eg, inactivated influenza and pneumococcal vaccines are allowed, but nasal influenza vaccination is not permitted).
11. Subject has received Bacillus Calmette-Guerin (BCG) vaccinations within 1 year prior to the Baseline Visit.
12. Subject has known tuberculosis (TB) infection, is at high risk of acquiring TB infection, or has current or history of nontuberculous mycobacterium (NTMB) infection. A subject with LTB (a positive interferon-gamma release assay [IGRA] and diagnosis confirmed by TB specialist) may be rescreened once and enrolled after receiving at least 8 weeks of appropriate LTB infection therapy and if no evidence of therapy-related hepatotoxicity has occurred prior to the first injection (alanine aminotransferase [ALT]/aspartate aminotransferase [AST] remain  $\leq 3$  times the upper limit of normal [ULN]).

Subject has a past history of active TB involving any organ system unless adequately treated according to World Health Organization/Centers for Disease Control (CDC) therapeutic guidance and proven to be fully recovered upon consult with a TB specialist.

Refer to [Section 12.3.1](#) for details on determining full TB exclusion criteria.

13. Subject has a history of a lymphoproliferative disorder including lymphoma or current signs and symptoms suggestive of lymphoproliferative disease.
14. Subject has any active malignancy or history of malignancy within 5 years prior to the Screening Visit EXCEPT treated and considered cured cutaneous squamous or basal cell carcinoma, or in situ cervical cancer.
15. Subject has a diagnosis of inflammatory conditions other than PSO or PsA, including but not limited to rheumatoid arthritis, sarcoidosis, or systemic lupus erythematosus. Subjects with a diagnosis of Crohn's disease or ulcerative colitis are allowed as long as they have no active symptomatic disease at Screening or Baseline.
16. Subject has had major surgery (including joint surgery) within the 3 months prior to the Baseline Visit, or has planned major surgery within 6 months after entering the study.
17. Subject has any systemic disease (ie, cardiovascular, neurological, renal, liver, metabolic, gastrointestinal, hematological, immunological, etc) considered by the Investigator to be uncontrolled, unstable, or likely to progress to a clinically significant degree during the course of the study.

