## **8.4 OLE2 Period**

### **8.4.1 OLE2 Screening (up to 4 weeks) – applicable for OLE2 Group B only**

Prior to any study specific activities of the OLE2 Period, subjects who completed the Week 144 Visit and are in the SFU or have completed the SFU of the OLE Period (OLE2 Group B subjects) will undergo screening. Subjects who have used systemic treatments after Week 144 must have stopped this treatment 1 month prior to receiving the first bimekizumab injection in the OLE2 Period. Screening procedures may be performed during this time. Subjects receiving systemic immunomodulatory medications for an indication other than PSO must have their eligibility confirmed by the Medical Monitor prior to enrollment in the OLE2 Period.

At the Screening Visit of the OLE2 Period (OLE2 Screening Visit), subjects will be asked to read, sign, and date an ICF that has been approved by the Sponsor and an IRB/IEC and that complies with regulatory requirements. Subjects will be given adequate time to consider any information concerning the study given to them by the Investigator or designee. As part of the informed consent procedure, subjects will be given the opportunity to ask the Investigator any questions regarding potential risks and benefits of continued participation in the study.

The following procedures/assessments will be performed at the OLE2 Screening Visit for subjects in the OLE2 Group B:

- Informed consent
- Inclusion/exclusion
- Urine drug screen
- Significant past medical history including clinically relevant past or coexisting medical conditions and surgeries (only applicable for subjects who completed the SFU, only new or modified medical history since completing the SFU should be entered in eCRF)
- AEs (only for subjects in the SFU)
- Physical exam
- Vital signs (sitting systolic and diastolic BP, pulse rate, and body temperature) should be obtained prior to blood sampling
- Collection of blood and urine samples for the following clinical laboratory tests:
  - Hematology and biochemistry
  - Urinalysis
  - Urine pregnancy test
  - Hepatitis B and Hepatitis C
  - HIV
- Tuberculosis questionnaire
- PASI
- Percentage of BSA

- 
- IGA
  - PHQ-9
  - eC-SSRS
  - Prior and concomitant medication (including new or modified medications initiated after SFU)
  - Contact IRT

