***Additional Procedures/assessments applicable for OLE2 Group A***

- Informed Consent
- ECG
- Blood sample for bimekizumab plasma concentrations
- Blood sample for anti-bimekizumab antibodies
- IGRA TB test
- scalp IGA
- mNAPSI
- pp-IGA
- EQ-5D-3L
- PASE
- PGADA
- WPAI-SHP V2.0

At the Week 144/OLE2 Baseline Visit, after completion of the above-mentioned procedures, administration of IMP will occur, preferably by self-injection under supervision of the site personnel.

Distribution of IMP and accountability activities for home administration to be performed as described in Section 7.2, Section 7.5, and Section 7.7.

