### 12.3 Other safety measurements

#### 12.3.1 Assessment and management of TB and TB risk factors

All subjects will be assessed for TB at Screening and at the time points specified in the Schedule of Assessments ([Table 5–1](#), [Table 5–2](#), and [Table 5-3](#)) through physical examination for signs and symptoms of TB, chest x-ray ([Section 12.3.1.2](#)), laboratory testing ([Section 12.3.1.1](#)), and subject questionnaire ([Section 12.3.1.3](#)).

[figure not shown]
For the purposes of this study, TB definitions are as follows:

- c. Known TB infection:
  - Active TB infection or clinical signs and symptoms suspicious for TB (pulmonary or extra-pulmonary).

- 
- History of active TB infection involving any organ system or findings in other organ systems consistent with TB infection, unless adequately treated and proven to be fully recovered upon consult with a TB specialist.
  - Any evidence by radiography or other imaging modalities consistent with previously active TB infection that is not reported in the subject's medical history.
- d. High risk of acquiring TB infection:
- Known close exposure to another person with active TB infection within the 3 months prior to Screening.
  - Time spent in a healthcare delivery setting or institution where individuals infected with TB are housed and where the risk of transmission of infection is high.
- e. Latent TB infection (unless appropriate prophylaxis is initiated at least 8 weeks prior to IMP dosing and continued to completion of prophylaxis):
- The absence of signs, symptoms, or physical findings suggestive of TB infection with a positive IGRA test (or 2 indeterminate IGRA test results) and a chest x-ray (or other imaging) without evidence of TB infection. If the result of the IGRA test is indeterminate, the particular IGRA test previously performed may be repeated once; if positive or indeterminate on retest, the subject may not be randomized to IMP without further evaluation by a TB specialist and discussion with the Study Physician, if LTBI is identified. The retest must be done during the protocol-defined Screening window.
- Note: If available, respiratory or other specimens must also be smear and culture negative for TB (CDC diagnosis of LTBI) <http://www.cdc.gov/TB/topic/testing/default.htm>.
- f. NTMB infection is defined as a clinical infection caused by mycobacterial species other than those belonging to the *Mycobacterium tuberculosis* complex.
- g. Tuberculosis test conversion:

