### **12.3.1.1 Tuberculosis assessment by IGRA**

During conduct of the study, the TB assessment by IGRA (QuantiFERON TB test is recommended) will be performed as described in [Table 5–1](#), [Table 5–2](#), and [Table 5-3](#) for all subjects. The test results will be reported as positive, negative, or indeterminate. Positive and indeterminate TB test results must be reported as an AE and appropriately updated once the final diagnosis is known (eg, active TB, latent TB, or false positive TB test). UCB also recommends that a TB specialist be consulted where TB (latent or active) is suspected or if there are doubts regarding test results. If active TB is identified, subject must undergo appropriate study-specified withdrawal procedures. The retest during Screening must be done during the protocol-defined Screening window.

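### OLE2 Group B: the visit lists give no IGRA before re-dosing, and exclusion 6.4.3 #4 stops at Week 144, so a subject can restart on the Week 144 test

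*Protocol*

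**What the plan says.** For OLE2 Group B, Section 6.4.3 has one TB-specific exclusion, #4: "Subject had a positive or indeterminate IGRA in the OLE study to Week 144, unless appropriately evaluated and treated as per Section 12.3.1". Its time limit is Week 144. Inclusion item 3 in 6.4.1, on withdrawal criteria, also looks only as far as Week 144.

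Section 8.4.1 introduces its list with "The following procedures/assessments will be performed at the OLE2 Screening Visit for subjects in the OLE2 Group B". The laboratory items are hematology and biochemistry, urinalysis, a urine pregnancy test, "Hepatitis B and Hepatitis C" and HIV. A TB questionnaire and a physical exam are also listed. There is no IGRA. The viral tests are tied to an eligibility rule, exclusion #11: "Subject has concurrent acute or chronic viral hepatitis B or C or HIV infection".

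In Section 8.4.2 the list common to Groups A and B has the TB questionnaire and physical exam but no IGRA. The IGRA appears only under "Additional Procedures/assessments applicable for OLE2 Group A". The next one listed for Group B is at OLE2 Week 48 (8.4.5), after the last dose at OLE2 Week 40.

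Section 12.3.1.1 says "the TB assessment by IGRA (QuantiFERON TB test is recommended) will be performed as described in" Tables 5-1, 5-2 and 5-3, for all subjects, so Table 5-3 matters. In the current text, the OLE2 Screening cell of its IGRA row is blank and the OLE2 Baseline cell reads Group A. In the copy in Section 18.9 (Protocol Amendment 5.4, Change #9), the OLE2 Screening cell reads Group B.

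**The concern.** Definition e in Section 12.3.1 describes latent TB as "The absence of signs, symptoms, or physical findings suggestive of TB infection with a positive IGRA test (or 2 indeterminate IGRA test results", with chest imaging that shows no TB. By that definition a questionnaire and a physical exam cannot find it, except through an exposure that the subject knows of and reports. Only the IGRA can.

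Group B has been off drug and possibly off study. Section 5.3 says that study time is not continuous for SFU completers, and it sets no limit on the gap. Section 5.8.1 accepts that these subjects may have had other treatments meanwhile. The plan repeats hepatitis and HIV testing for them and makes the results exclusionary, but its visit lists do not do the same for TB. Group A, which was never off study, has an IGRA at the visit of its first OLE2 dose.

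At stake is the safety of a subject infected during the break who has no symptoms and no known contact. A site working from 8.4.1 and 8.4.2 would restart an immunomodulator in that subject.

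**Working it through.** All times are nominal; visit windows are ignored.

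**Inputs.** Entry Screening up to 5 weeks (8.1). Last OLE dose at Week 136 (5.2.3). SFU Visit 20 weeks after the last dose (5.3). OLE2 Screening up to 4 weeks (8.4.1). Last OLE2 dose at OLE2 Week 40. IGRAs at Screening and Weeks 44, 96 and 144 (8.1, 8.2.12, 8.3.7, 8.3.8), then OLE2 Week 48 (8.4.5).

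**1. Reproduce the durations in 5.3.**
- Direct roll-over: 5 + 144 + 40 + 20 = 209 weeks, as stated.
- The SFU ends 136 + 20 − 144 = 12 weeks after Week 144. Adding this and OLE2 Screening gives 209 + 12 + 4 = 225 weeks, as stated.

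So the 225 weeks leave out any off-study time between the SFU and OLE2 Screening.

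**2. Age of the Week 144 IGRA at the first OLE2 dose, if none is done at OLE2 Screening.**
- SFU completer with no off-study time: 12 + 0 = 12 weeks to 12 + 4 = 16 weeks.
- Subject still in the SFU: up to 12 + 4 = 16 weeks.
- SFU completer with G weeks off study and full OLE2 Screening: 16 + G. G is not given. Assuming G = 12, 26 or 52, the age is 28, 42 or 68 weeks.

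**3. Gap from the Week 144 IGRA to the next one (OLE2 Week 48).**
- SFU completer with no off-study time: 12 + 48 = 60 to 16 + 48 = 64 weeks.
- Still in the SFU: 48 to 64 weeks.
- With the same assumed G: 64 + G = 76, 90 or 116 weeks.

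**4. Earlier IGRA intervals in the plan.** Screening to Week 44: 44 + 2 = 46 to 44 + 5 = 49 weeks. Then 96 − 44 = 52 and 144 − 96 = 48 weeks. The Week 144 test is therefore older at re-dosing than the longest of these only if 16 + G > 52, that is, G > 36 weeks with full screening.

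**5. Can the blank cell in the current Table 5-3 be trusted?** Sections 8.4.4 and 8.4.5 require PASI, BSA, IGA and the TB questionnaire at OLE2 Weeks 12, 24, 36 and 48. The current table shows two post-baseline marks for each of these rows. Its hematology and urinalysis rows lack the Week 24 mark that 8.4.4 requires. Marks have been lost from that page, so a lost Group B entry in the IGRA row is quite possible. The Section 18.9 copy has that entry. The prose lists are the firmer evidence: 8.4.1 and 8.4.2 give Group B no IGRA, either in the body or as reproduced in Section 18.9.

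**6. With an IGRA at OLE2 Screening.** The result is at most 4 weeks old at re-dosing, and the next gap is 48 to 48 + 4 = 52 weeks, within the range in step 4.

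**The case against.** The best defence is that Table 5-3 governs IGRA timing through 12.3.1.1, that its current copy is damaged, and that the Amendment 5.4 copy schedules the test for Group B. On that reading there is no re-dosing on an old test, only an item missing from a list. This is plausible, and it is why the point cannot be put as a certain absence of the test. It does not clear the plan. Section 8.4.1 would then disagree with the table, and #4 would still not name the new result.

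A reader might go further in four ways that the documents do not support.

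- *Group B restarts with no TB check.* Not so. The SFU Visit (8.6) has a TB questionnaire and an exam covering TB signs and exposure risk. The questionnaire is repeated at OLE2 Screening, at OLE2 Baseline and at the 12-weekly visits.
- *A positive OLE2 Screening IGRA would be ignored.* Not so. Definition g in 12.3.1 requires IMP to stop and a specialist referral on conversion. Withdrawal criterion 9a stops IMP for suspected new latent TB. Section 12.3.1.4 bars IMP until active TB is excluded and prophylaxis has run 4 weeks. Exclusion #2 in 6.4.3 also gives the investigator discretion. These rules act on a conversion once a test shows it; they do not order the test.
- *The IGRA will be a year or more old.* That rests on assumed off-study times. Without an assumption, only the 12-to-16-week minimum for completers and the 16-week maximum for subjects in the SFU can be stated. The plan already doses continuing subjects between IGRAs up to 52 weeks apart.
- *Group B needs entry exclusion #12 ("Subject has known tuberculosis (TB) infection, is at high risk of acquiring TB infection, or has current or history of nontuberculous mycobacterium (NTMB) infection") carried over, and a new rule for a reported contact.* Both are optional. The during-study route in 12.3.1.3 and 12.3.1.4 already gives a workable answer.

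**Conclusion.** The point holds in limited form. The visit lists for Group B contain no IGRA before the first OLE2 dose, and exclusion #4 considers results only through Week 144. Followed as written, they permit re-dosing of a subject with new asymptomatic latent TB on the Week 144 test. The age of that test is as in step 2 of the working, and for SFU completers it has no stated upper limit.

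The conclusion assumes a nominal last OLE dose at Week 136 and a site that works from 8.4.1 and 8.4.2. If Table 5-3 does schedule the test at OLE2 Screening, the interval problem disappears. What remains is an omission in 8.4.1 and an exclusion that does not name the result. A correction is needed on either reading.

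The number of Group B subjects is not given, so the number exposed cannot be estimated. The Week 16 and Week 48 analyses are unaffected.

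**What to change.** 1. In 8.4.1, add an IGRA to the Group B laboratory tests at OLE2 Screening, and state that the result must be available before the first OLE2 dose. Confirm the matching entry in Table 5-3.
2. In 6.4.3, extend exclusion #4 to a positive or indeterminate IGRA at OLE2 Screening, and keep its present exception for subjects evaluated and treated under 12.3.1.

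The cost is a few sentences and one extra assay per Group B subject, at a visit where blood is already drawn for hematology, hepatitis and HIV. The result has to come back within the OLE2 Screening window of up to 4 weeks. Positive or indeterminate results will need a TB specialist referral and may delay or prevent re-entry for those subjects.
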